Design: Pilot of novel care model for low-barrier care and adherence support for uptake and sustained use of biomedical HIV prevention and medications for opioid use disorder for women who inject drugs

Study Population: 50 female-identifying people ≥18 years of age and older who have ever injected drugs and are not known to be HIV-positive

Study Site: Community-based clinic on north Aurora Avenue in Seattle, WA

Primary Study Objectives:

1. Evaluate uptake of PrEP and MOUD
2. Evaluate sustained use of PrEP and MOUD
3. Evaluate treatment completion rate and time to completion after POC STI testing
4. Assess acceptability of pilot community-based care model
5. Assess acceptability of POC STI testing at community-based site.

Approach: We will conduct a pilot study of a community-based novel care model developed with community feedback and a community advisory board (CAB) co-design process during phase I of this project. We will enroll 50 female-identifying people and follow them for 6 months. We will assess uptake of PrEP and buprenorphine; POC STI testing and treatment completion rates; sustained use of PrEP and buprenorphine at months 3 and 6 (n=50). We will conduct surveys, guided by CFIR, to assess and characterize the acceptability and feasibility of venue-based primary and HIV prevention care among women who inject drugs (WWID).

Background and rationale

Women who inject drugs (WWID) experience frequent barriers to receiving primary care, especially sexual health and addiction services, because of perceived stigma, competing needs, and structural inequities within the healthcare system. Barriers to care among WWID are often exacerbated by the additional social chaos of unstable housing and engagement in transactional sex. These structural realities promote exclusion from traditional primary care systems, increase risk of HIV acquisition, and have led to rising rates of syphilis infections and overdose deaths among WWID in recent years. PrEP, buprenorphine, and STI control are key components of the End the HIV Epidemic prevention pillar and proven tools for reducing risk of HIV acquisition and opioid overdose, but uptake and sustained use of these interventions are low among WWID.

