Pre-exposure prophylaxis (PrEP), buprenorphine, and sexually transmitted infection (STI) control are proven interventions for reducing risk of HIV acquisition, but their use among WWID remains low. PrEP reduces HIV acquisition among women, including WWID, and the Centers for Disease Control and Prevention (CDC) recommend the use of PrEP in PWID who share injection equipment and/or have overlapping sexual risk factors. Nevertheless, multiple U.S. cities report extremely low rates of PrEP use among PWID, ranging from 0 – 3%. Similarly, results of a recent systematic review revealed that PrEP uptake among PWID was low, between 0 – 3% across 23 studies, despite this populations' high willingness to use PrEP. Despite this, there are currently no recommendations or guidelines for how to best support PWID, in particular WWID, with PrEP use and adherence. Most domestic studies on PrEP for PWID characterized awareness

of, interests in and determinants of PrEP use, but lack novel interventions to improve PrEP uptake and sustained use. Medications for opioid use disorder (MOUD), including buprenorphine, similarly reduce the risk of HIV acquisition in WWID through a reduction in both needle-sharing and sexual risk behaviors. However, women are under-represented in both inpatient and outpatient substance use treatment programs, and, in comparison to their cisgender male counterparts, women delay treatment until further on in their addiction. The provision of low-barrier buprenorphine can improve uptake; however, sustained use of buprenorphine, and rates of adherence and retention in care may be less than 50% at 6 months across all genders of PWID. In addition to PrEP and MOUD, robust data supports the use of STI control in HIV prevention, due to the substantial increased risk of HIV acquisition associated with STI coinfection. Despite the existence of proven interventions, comprehensive sexual and reproductive healthcare tailored to WWID is lacking, even among those who exchange sex and experience high rates of STIs. Point-of-care (POC) testing provides an important opportunity to leverage venue-based healthcare to provide comprehensive services on a walk-in basis. The use of rapid POC STI testing nearly eliminates issues with patient loss to follow-up and incomplete or missing treatment, which continues to be a problem for STI case-detection based public health efforts.

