Clinical study visits will occur at enrollment, a follow-up study visit at month-3, and an exit visit at 6-months post-enrollment. For participants who are prescribed buprenorphine, additional brief refill visits will occur at monthly intervals. All assessments will occur during in-person visits in the pilot clinic. Each study visit will consist of a short survey, an eligibility assessment for oral PrEP and MOUD, standard clinical care, and biological sample collections (i.e., DBS sample collection for research only, self-collected vaginal swabs for point-of-care STI testing, and blood samples for blood born infection testing). To test the impact of this pilot clinic model on improving uptake and sustained use of HIV prevention services, we will utilize medical record data and DBS drug (buprenorphine and tenofovir) levels. Prior to enrollment, participants will be asked to provide consent for participation in the study, review of electronic medical record (EMR) data, and review of pharmacy records. Consent will be collected using electronic data capture (REDCap) and participant data will be collected by medical record number (MRN) utilizing an EMR querying technology (Leaf) generated by the University of Washington as well as manual chart review. Participants meeting CDC eligibility criteria for PrEP will be counselled on HIV risk, offered HIV testing, and if negative and interested, oral PrEP will be prescribed per clinical guidelines. Additionally, participants with active self-reported use of opioids will be counselled on options for opioid use disorder treatment, and those interested in MOUD, will be provided with a prescription for buprenorphine-naloxone or buprenorphine, per clinical guidelines. Uptake of PrEP and buprenorphine will be measured by review of pharmacy and EMR records and will be defined by filling a prescription for PrEP or buprenorphine. In collaboration with [name] and the University of California San Francisco (UCSF) Hair Analytical Laboratory (HAL), we will measure sustained use of PrEP and buprenorphine via tenofovir disoproxil fumarate (TDF) and buprenorphine levels in samples of 150 hairs. The UCSF-HAL can simultaneously test for buprenorphine, fentanyl, and tenofovir from the same specimen, and we will measure these drug levels at 3- and 6- months to evaluate adherence to PrEP and buprenorphine. Additionally, dried blood spots (DBS) will be collected and archived to ensure that drug levels are collected during this study in the event there are any complications with hair testing.

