
At each visit, brief demographic and behavioral surveys will be administered to women enrolled in the study via tablets, with responses recorded in REDCap. At the end of each visit an additional survey assessing acceptability of venue-based care will be administered to each participant. Questions will be informed by the CFIR and designed to assess the acceptability and relative priority of venue-based primary and HIV prevention care among women seeking services. *As part of an assessment of* acceptability, questions will also focus on the perceived stigma associated with receipt of care at the pop-up van clinic near a venue for drug use and exchange sex. Following completion of the intervention, information on feasibility, implementation barriers and facilitators will be collected using semi-structured interviews with

clinical staff to contextualize logistical and structural barriers faced by venue-based service delivery.

Screening and Recruitment

Overview of screening and recruitment

Flyers advertising the venue-based clinic will be posted at local harm-reduction and social service sites: the Aurora Commons, People's Harm Reduction Alliance, Mary Pilgrim Inn, The Gateway, WeCare Methadone Clinic, and at other locations within the community, based on the suggestions of the community advisory board. All women who present to the venue-based clinic will be screened for possible enrollment using a brief survey programed into REDCap.

Screening surveys will be self-administered, unless the participant requests that a clinic team member assist them in filling out responses to screening questions. Women who meet inclusion criteria will be provided with brief information about the study and asked if they would like to learn more. Women who express interest in the study will then be connected to the research assistant, who will explain the study in more detail and go through the informed consent process. Women who agree to participate will provide informed consent via REDCap on a study tablet housed within the clinic. Women who are ineligible for the study, or those who do not wish to participate, will still be allowed to access standard of care medical services within the venue-based clinic.

Screening questions

1. How old are you?
2. What's your gender identity?
3. Have you ever injected drugs, even just once, in your lifetime?
4. Have you ever been tested for HIV?
 - a. If yes, when and what was the result?

Inclusion Criteria

- ≥18 years of age

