 - b. Participants who accept prescriptions for MOUD at multiple points throughout the study will only be counted once when calculating uptake.
 - c. Final analysis will present uptake as a percentage (proportion).
3. Evaluate sustained use of PrEP
 - a. PrEP: Dried blood spot (DBS) samples were obtained at each visit to assess PrEP adherence via tenofovir-diphosphate (TFV-DP) concentrations. Sustained use was defined as >4 doses/week, resulting in a DBS TFV-DP concentration of >700 fmol/sample at 3 and/or 6 months post-enrollment among those prescribed PrEP at a preceding study visit.
 - b. Final analysis will present sustained use for both PrEP as a percentage (proportion).
4. Evaluate sustained use of MOUD
 - a. MOUD: DBS samples were obtained at each visit to assess MOUD adherence via buprenorphine and norbuprenorphine concentrations, both measured in ng/mL. Sustained use was defined as any buprenorphine and/or norbuprenorphine detected, resulting in a DBS >0 ng/mL concentration of buprenorphine and/or norbuprenorphine at 3 and/or 6 months post-enrollment among those prescribed MOUD at a preceding study visit.
 - b. Final analysis will present sustained use for MOUD as a percentage (proportion).
5. Evaluate STI treatment completion rate and time to completion after POC STI testing
 - a. Treatment completion will be defined as documented treatment following a reactive POC STI test (chlamydia, gonorrhea, syphilis, and/or trichomonas). Treatment will either be indicated in the Visit Clinical Summary from the study visit or noted during medical record chart review by a study provider. If treatment

was not provided on the same day as the visit, the date of treatment will be documented in the study database.

- b. Final analysis will present the treatment completion rate as the proportion of STIs where treatment was documented, by all STIs and by type.
 - c. Final analysis will present the time to treatment completion as the proportion of STIs treated same-day. Of the STIs not treated same-day, time to treatment will be presented as median number of days with an interquartile range.
6. Assess acceptability of pilot community-based care model
- a. Participants completed an acceptability survey following each study visit. Acceptability will be presented by study visit (i.e., enrollment, Month 3, and Month 6) as a proportion of all enrolled participants (N=50) who responded to the following questions:

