 - i. "I feel confident that my health is improved by getting care in a mobile clinic." (Agree, Somewhat agree)
 - ii. "I feel safe getting care in a mobile clinic." (Agree, Somewhat agree)
 - iii. "I am worried about how people will react if they see me getting care at a mobile clinic." (Disagree, Somewhat disagree)
7. Assess acceptability of POC STI testing at community-based site.
- a. Participants completed an acceptability survey following each study visit. Acceptability will be presented by study visit (i.e., enrollment, Month 3, and Month 6) as a proportion of all enrolled participants (N=50) who responded to the following questions:
 - i. "I felt comfortable getting rapid STI testing in the mobile clinic." (Agree, Somewhat agree)
 - ii. "I prefer getting rapid tests for sexually transmitted infections (STI) more than getting traditional STI tests." (Agree, Somewhat agree)

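### Acceptability at each visit is given a fixed denominator of 50, although only women who attend that visit can answer the survey

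*Protocol*

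**What the plan says.** The synopsis of the protocol lists acceptability of the care model and acceptability of point-of-care (POC) STI testing as the fourth and fifth of five primary objectives. The planned cohort is stated there too: "We will enroll 50 female-identifying people and follow them for 6 months".

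The Analysis Plan handles the two objectives in items 6a and 7a with the same wording. On timing: "Acceptability will be presented by study visit (i.e., enrollment, Month 3, and Month 6"). On the denominator: "as a proportion of all enrolled participants (N=50) who responded to the following questions". Survey statements follow, each with the answers that count as favourable in brackets. These are the two agreeing categories, except for the statement about worry over other people's reactions, where the two disagreeing categories count.

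How the answers are obtained is set out under Data Collection Overview: "All assessments will occur during in-person visits in the pilot clinic", and "At the end of each visit an additional survey assessing acceptability of venue-based care will be administered to each participant". The protocol states no expected attendance at Month 3 or Month 6. Items 6 and 7 give no rule for a participant without a survey at a visit.

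**The concern.** The denominator is fixed at everyone enrolled, but the measurement exists only for those who come and stay to the end of the visit. The protocol itself foresees absences. Under Incarcerated Participants, women are temporarily withdrawn while incarcerated and staff follow up missed appointments. Under Adequacy of Protection Against Risks, a participant may leave a visit at any time, which could be before the survey.

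For the acceptability items a missing survey is an absent opinion, not an unfavourable one. If it is counted in the 50 without comment, the figure mixes two quantities: how many women returned, and what those who returned thought. For the worry statement, an absent woman would be counted with those who did not deny being worried.

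Two of the five primary objectives rest on these proportions. Under Importance of Knowledge to be Gained, the protocol says the study will inform on acceptability and that a demonstrated benefit would support study at scale. A low percentage that partly reflects attendance could be misread as a poor opinion of the clinic.

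**Working it through.** **Inputs**

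- Denominator N = 50 at all three visits: Analysis Plan, items 6a and 7a.
- Numerator: favourable answers listed under items 6a and 7a.
- Who can answer: attendees only, at the end of the visit (Data Collection Overview).
- Attendance at Month 3 and Month 6: not stated, so assumed here from 40% to 100%.
- Acceptability among respondents: not stated, so assumed constant at 80%. All attendees are assumed to answer.

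The protocol has no sample-size calculation, target acceptability or retention figure to reproduce. The check is direct arithmetic on the stated rule.

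**Step 1: two readings of the sentence.** Let m be the number answering at a visit and a the proportion of them giving a favourable answer.

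- Reading A, 50 as denominator: reported figure = (a × m) / 50.
- Reading B, respondents as denominator: reported figure = (a × m) / m = a.

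Reading A is the more natural. The bracketed answers complete the phrase about responding and so define the numerator, and a single N is printed for all three visits. Under reading B the denominator is m, so the printed N=50 is false whenever m is below 50. The readings agree only when m = 50.

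**Step 2: ceiling under reading A.** Setting a = 1 gives m/50. If every attendee is favourable, 80% attendance gives 40/50 = 80%, 60% gives 30/50 = 60%, 50% gives 25/50 = 50% and 40% gives 20/50 = 40%. The highest figure that can be reported is the response rate.

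**Step 3: constant opinion, a = 80%.**

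| Attendance | m | Favourable | Reading A | Reading B |
|---|---|---|---|---|
| 100% | 50 | 40 | 40/50 = 80% | 40/50 = 80% |
| 80% | 40 | 32 | 32/50 = 64% | 32/40 = 80% |
| 60% | 30 | 24 | 24/50 = 48% | 24/30 = 80% |
| 50% | 25 | 20 | 20/50 = 40% | 20/25 = 80% |
| 40% | 20 | 16 | 16/50 = 32% | 16/20 = 80% |

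**Step 4: exact (Clopper-Pearson) 95% intervals.** At 80% attendance they are 49% to 77% for 32/50 and 64% to 91% for 32/40, which overlap. At 50% attendance they are 26% to 55% for 20/50 and 59% to 93% for 20/25, which do not. This is not a test, since both come from the same answers. It shows that the choice of denominator can matter more than sampling error.

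**Step 5: comparison with the other items.** For uptake (items 1a and 2a), 50 is a coherent denominator: a woman who never returns has in fact not accepted a prescription from the study team at the later visits. Sustained use (items 3a and 4a) is limited to those prescribed the drug at a preceding visit. Only items 6a and 7a pair the full enrolled number with an opinion that has to be collected in person. The enrollment visit is little affected, because the baseline visit follows consent immediately.

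**The case against.** The best defence is that the sentence does refer to participants who responded, so an analyst could use respondents as the denominator and the distortion would not occur. That is a fair limit. A reader might infer that loss to follow-up will certainly be reported as falling acceptability, and the text does not settle that. The defence still leaves an N=50 that is wrong at any visit with a missing response, so the sentence needs correcting on either reading.

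A second defence is that counting non-response as unfavourable is a recognised conservative choice. It is, when it is labelled as such. Here it is not labelled, and no respondent figure is planned beside it.

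A third is that reporting response counts is commonly left to a statistical analysis plan, which is not at hand. That would answer a complaint about missing table detail. It does not answer a denominator that the protocol itself prints.

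Three stronger readings are tempting, and the protocol does not support them:

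- **Expected attendance below one half.** Background and rationale says "rates of adherence and retention in care may be less than 50% at 6 months across all genders of PWID". That sentence is about buprenorphine care among people who inject drugs in general. It is not a forecast of attendance at this study's visits, which carry a $25 payment each.
- **Untested women diluting item 7.** Table 1 schedules the POC tests at months 0, 3 and 6 for every participant, without the footnote for clinical indication. The section on follow-up visits says the same. Untested attendees are therefore not a planned group, and the statement on preferring rapid tests does not depend on a test that day.
- **An invalid comparison between visits.** The plan presents three descriptive percentages and specifies no test or trend. Readers may compare them informally, but the protocol makes no claim of change.

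**Conclusion.** The point holds as a fault in a stated denominator. Followed in its most natural sense, the rule counts each missed survey as an unfavourable opinion and caps reported acceptability at the response rate. Followed in the other sense, it prints the wrong N.

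The size depends on attendance, which the protocol does not give. Under an assumed constant 80% among respondents, the understatement is 16 percentage points at 80% attendance, 32 at 60% and 40 at 50%. It is nil if every participant answers at every visit. These are illustrations over an assumed range, not predictions. The need for correction does not depend on which of them is closest.

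**What to change.** In items 6a and 7a, define the proportion for each statement and visit as favourable answers divided by the participants who answered that statement at that visit. Print beside it the number responding out of 50. If the N=50 version is kept, label it as a lower bound in which missing answers are counted as not favourable.

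The cost is a change of wording and one table column. No new data, visits or participants are needed.

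There is a small downside: women who keep attending may be the more satisfied ones, so a respondent-only figure can flatter the clinic. That is why the response count must stand next to every percentage. With the lower bound also shown, a reader can see how far the conclusion depends on those who did not answer.
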